8.4 Safety Data

Safety data will be summarized for each Subject enrolled in the study.

9. Administrative Issues

9.1 Changes to the Protocol

Any change or addition to this protocol requires a written protocol amendment that must be approved by the Aspire IRB before implementation. Only in the event of an emergency should a deviation from the protocol occur for an individual Subject. Such a deviation will be for the Subject in the emergency situation and for that Subject only. A description of the deviation from the protocol and the reason for it will be recorded in the source documents.

9.2 Monitoring Procedures

The Principal Investigator and site personnel will complete all CRFs in a timely manner following completion of each Subject visit to facilitate documentation of study procedures and review of the CRFs.

9.3 Access to Data Source/Documentation

The Principal Investigator will permit representatives of the Aspire IRB and/or the FDA (or other regulatory authority) to inspect the facilities and records relevant to this study, including Subject charts, either during the study or after its completion.

9.4 Quality Control and Quality Assurance

The Principal Investigator must provide the documents listed below before drug can be shipped and the study initiated:

- Original Form FDA 1572 completed and signed by the Principal Investigator;
- Current medical license for each physician appearing on Form FDA 1572;
- Copy of IRB correspondence documenting approving the protocol, informed consent form, recruitment materials and any instructions for the Subject regarding the procedure, and any other documents reviewed and/or required by the IRB.

9.5 Ethics

This study will be conducted in accordance with current Good Clinical Practice (GCP), with the Code of Federal Regulations (CFR Title 21, Parts 50, 54, 56, 312, and 314). Current GCP is consistent with the ethical principles described in the current version of the Declaration of Helsinki.

Requirements for Independent Review Board (IRB) review and obtaining informed consent are described in Sections 3.3 and 5.1, respectively.

9.6 Case Report Forms, Data Handling, and Recordkeeping

The following procedures will be employed related to recording of data:

- Relevant information determined at each Subject visit is to be recorded on source documents/CRFs.
- Data recorded on CRFs will be documented in an anonymous fashion with the Subject identified only by her Subject number and initials.
- All CRFs are to be completed in a neat, legible manner to ensure accurate communication of data. A black pen is preferred to ensure clarity of any reproduced copies. Any change or corrections made on the CRFs must be dated and initialed by the person making the change. In such cases, the best procedure is to cross out the original entry with a single line. Do not erase, overwrite, or obliterate, by any means, the original entry.
- CRFs and any data queries should accurately reflect Subject data records (source documents).
- The completed CRF set for each Subject is to be reviewed by the Principal Investigator for completeness and accuracy. The Principal Investigator will sign and date the last CRF page to indicate this review was performed.

Appendix 1: Schedule of Study Procedures

Study DAY:	Up to -28	0	28 ± 7	56 ± 7	84 ± 7	112 ± 7	140 ± 7 or ET
Visit	1	2	3	4	5	6	7
Procedure							
ICF & HIPAA	X						
I/E Criteria	X	X					
Medical history	X	X					
Physical exam	X						X
Breast/Gyn exam	X						X
Vital signs	X	X	X	X	X	X	X
Height & weight	X						X
Concomitant Medications	X	X	X	X	X	X	X
Pain scale	X	X	X	X	X	X	X
Clinical laboratory tests ²	X						X
Vulvoscopy with photography	X	X	X	X	X	X	X
Visual Scale	X	X	X	X	X	X	X
Q-tip test	X	X	X	X	X	X	X
Dispense study drug		X	X	X	X	X	
Dispense diaries		X	X	X	X	X	
Dispense lubricant		X	X	X	X	X	
Collect/reconcile medication			X	X	X	X	X
Calculate compliance			X	X	X	X	X
Collect diaries			X	X	X	X	X
Collect AE data	X	X	X	X	X	X	X

ET = early termination

For detailed study procedures, see Section 5, Clinical Procedures.

Appendix 2: Pain Scale

Appendix 3: Visual Scale

Observation	0 - none	1 - mild	2 - moderate	3 - severe
Petechiae				
Pallor				
Friability				
Dryness				
Redness				

Appendix 4: Diary

Initials _____ Number _____ Date _____

Please complete after each sexual event, answering all questions.

If you experienced dryness before were you less dry? Yes No N/A

Did you use lubricant during this activity? Yes No

Did you experience pain/discomfort during foreplay? Yes No N/A

Did you experience pain during masturbation? Yes No N/A

Did you experience pain during oral sex? Yes No N/A

Did you experience pain during intercourse? Yes No N/A

Did you stop early because of discomfort? Yes No

AN OPEN-LABEL PILOT PROSPECTIVE VULVOSCOPY WITH PHOTOGRAPHY  
STUDY OF THE VISIBLE CHANGES IN THE VULVA, VESTIBULE AND VAGINA PRE-  
AND POST- TWENTY WEEKS OF DAILY ADMINISTRATION OF 60 MG  
OSPEMIFENE IN POST-MENOPAUSAL WOMEN WITH DYSPAREUNIA FROM  
VULVAR VAGINAL ATROPHY

NCT 02784613  
April 4, 2016

Each subject's baseline and end of the study vulvoscopic photographs were subsequently assessed using a four-point rating scale, the vulvoscopic genital tissue appearance (VGTA) scale. The VGTA scale has not been validated. This scale assesses ten different parameters of the appearance of the genital tissue including loss of labia majora, loss of labia minora, decreased size of glans clitoridis, prominence of urethral meatus, stenosis of introitus, vestibular pallor, vestibular erythema, loss of vestibular moisture, loss of vaginal rugae, and loss of prominence of the anterior vaginal wall (Table 2). Each subject could score between 0 and 30 total points on the VGTA at each visit. A higher score of the VGTA scale was considered consistent with a worse vulvoscopic genital tissue appearance.

Baseline physical examination was performed as part of the screening. The physical exam included performance of a cotton-tipped swab testing where the examiner applied gentle pressure at each location of the vestibule: 1:00, 3:00, 5:00, 6:00, 7:00, 9:00, and 11:00 o'clock. The subject was asked to rate her pain on a scale from 0 to 3. Aggregate pain scores at baseline and study end were compared using the Wilcoxon signed-rank test.

Baseline sexual function diary data concerning dryness and sexual pain were collected. The questions of the sexual function diary have not been validated. For 4 weeks prior to each study visit, subjects recorded yes or no answers to the following questions for each sexual encounter: 1) did the subject experience dryness before and were you now less dry, 2) did the subject use lubricant during this sexual activity, 3) did the subject experience pain/discomfort during foreplay? 4) did the subject experience pain during masturbation, 5) did the subject experience pain during oral sex, 6) did the subject experience pain during intercourse, and 7) did the subject stop early because of discomfort. Diaries were collected and new ones administered at each subsequent visit. The number of total sexual events, as well as percentage of total sexual events with pain or lubrication difficulty was compared for diaries collected at week 0 and week 20 using the Wilcoxon signed-rank test.

At the completion of the study, the photographs were sorted by subject number and date of exam and assessed by the principal investigator, a sexual medicine physician, who had not examined any of the women in person. He assigned scores to the photographs using pre-determined Likert scales for the 10 parameters of VGTA scale (Table 2). Differences in pre-and post-treatment scores were compared using Wilcoxon signed-rank test for non-parametric matched pairs. All tests of significance were 2-tailed with  $p < 0.05$  considered significant. All analyses were performed in Stata®, version 13.

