2. TRIAL OBJECTIVE

The primary objective of this study is to prospectively document, using vulvoscopy with detailed photography, the visible changes to the vulva, vestibule and vaginal region in post-menopausal women with dyspareunia taking 60 mg daily ospemifene for twenty weeks at 6 timepoints: baseline, 4 weeks, 8 weeks, 12 weeks, 16 weeks and 20 weeks.

Secondary objectives include changes in pain as noted on the pain scale (appendix 2) and the q-tip test, in the vestibule on visual scale (appendix 3) by the clinician and sexual function by subject diary (appendix 4).

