3.4 Rationale for Study Design and Subject Selection

Currently there have been limited prospective studies using vulvoscopy with detailed photography demonstrating visible changes to the vulva, vestibule and vagina following oral administration of 60 mg ospemifene in post-menopausal women with VVA and dyspareunia. Information regarding visible changes to the vulva, vestibule and vagina may be very important to the patient and to the health care provider to best understand the beneficial effects of ospemifene and to ensure patient compliance with treatment.

This study is being conducted in an unblinded fashion because the primary endpoint is a collection of photographs. All subjects will receive the same active drug at the same dosage.

4. Selection and Withdrawal of Subjects

The study population will include menopausal females with vulvar vaginal atrophy (VVA) causing dyspareunia.

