8.1 Determination of Sample Size

The sample size of 10 menopausal Subjects was chosen for this study based on this being a pilot study and this sample size will be sufficient to prospectively document visible changes to the vulva, vestibule and vagina in post-menopausal women with VVA and dyspareunia. There will be a total of 6 photographic sessions of the vulva, vestibule and vagina over the 20 weeks of the study. The photograph(s) at baseline (vulvoscopy session 0) will be compared to photographs at 4 weeks (vulvoscopy session 1), 8 weeks (vulvoscopy session 2), 12 weeks (vulvoscopy session 3), 16 weeks (vulvoscopy session 4) and 20 weeks (vulvoscopy session 5).

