8.2 Photographic Data

Changes to the vulva, vestibule and vagina will be examined prospectively by comparing photographs of post-menopausal women with VVA and dyspareunia at 4 weeks, 8 weeks, 12 weeks, 16 weeks and 20 weeks while on treatment with 60 mg ospemifene. The proportion of subjects with improvement will be tabulated by scheduled visit.

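### The protocol compares baseline photographs with each of weeks 4 to 20, but the SAP describes scoring only at baseline and end of study; improvement, the weeks 4 to 16 photographic field and the baseline visit also need settling

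*SAP*

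**What the plan says.** **Protocol, timepoints and comparison.** The primary objective (Section 2) is to document visible change in women "taking 60 mg daily ospemifene for twenty weeks at 6 timepoints: baseline, 4 weeks, 8 weeks, 12 weeks, 16 weeks and 20 weeks". Section 8.1 carries this into the comparison: "The photograph(s) at baseline (vulvoscopy session 0) will be compared to photographs at 4 weeks (vulvoscopy session 1"), and likewise weeks 8, 12, 16 and 20. Section 8.2 gives the summary: "The proportion of subjects with improvement will be tabulated by scheduled visit". Section 3.4 states that "the primary endpoint is a collection of photographs".

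**SAP, scoring and test.** Each subject's "baseline and end of the study vulvoscopic photographs were subsequently assessed using a four-point rating scale", the 10-item VGTA, on which a higher score is worse. The range is given as "Each subject could score between 0 and 30 total points on the VGTA at each visit". When the study was complete, "the photographs were sorted by subject number and date of exam" and then scored by one reader. The only photographic test is this: "Differences in pre-and post-treatment scores were compared using Wilcoxon signed-rank test for non-parametric matched pairs". The SAP contains no by-visit photographic summary and no proportion improved.

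**Photographic field.** Sections 1, 3.1, 8.1 and 8.2 refer to vulva, vestibule and vagina throughout, as do the visit lists for screening (5.2), Day 0 (5.4) and week 20 (5.6). Section 5.5, which covers weeks 4 to 16, names only the vulvar vestibule.

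**Baseline.** Sections 5.2 and 5.4 and Appendix 1 schedule photography at both screening and Day 0. Sections 1 and 8.1 number the baseline as session 0, and Section 3.1 numbers it as session 1. None of them gives a visit number.

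**The concern.** The by-visit photographic comparison is the stated purpose of the study, yet the analysis document describes a measure for one of its five parts. Three things follow.

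- The Section 8.2 table has no stated measure at weeks 4 to 16 and no rule for who counts as improved at any visit. A rule chosen after the photographs have been seen, on a scale that the SAP says is unvalidated, in an open-label study without a control group, would be hard to defend.
- If staff follow Section 5.5 to the letter, vaginal images may not be taken at four visits, and images not taken cannot be recovered later.
- With two pre-dose photograph sets and no named baseline, the reference image for every comparison is open to choice.

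**Working it through.** N = 10 is a pilot choice with no effect size, standard deviation or power behind it, so there is no sample-size figure to reproduce. The check is a count and a comparison of texts.

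**1. The SAP's scale range.** Ten items, each 0 to 3: 10 × 3 = 30. This agrees with the stated maximum.

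**2. Planned against described scoring.** Inputs: 10 women (Section 8.1), six timepoints (Section 2), and two scored timepoints (SAP).
- Planned subject-timepoints: 10 × 6 = 60.
- With a described score: 10 × 2 = 20.
- Without one: 60 − 20 = 40, and 40/60 = 67%.
- Planned comparisons with baseline: 5. Described: 1 (week 20). Not described: 4.

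The result does not depend on which pre-dose visit is the baseline. If it is Day 0, the six timepoints are Day 0 plus weeks 4 to 20. If it is screening, they are screening plus weeks 4 to 20. Either way two of the six are scored.

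**3. Is improvement defined elsewhere?** Section 8.3 sorts women into worsened, unchanged and improved, but for each item of the clinician's visual scale, not for photographs. The VGTA text gives a direction only.

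**4. The Section 5.5 field read literally.** Two VGTA items are vaginal (rugae, and prominence of the anterior wall): 2 × 3 = 6 of 30 points. Without vaginal images the maximum at weeks 4 to 16 would be 30 − 6 = 24, and a total from those visits could not be compared with a 30-point baseline.

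**5. Which visit is baseline?** Appendix 1 marks vulvoscopy with photography at Visits 1 to 7, which is seven visits. Sections 1 and 8.1 state six sessions, so one pre-dose set falls outside the count.
- For Day 0: six sessions are placed within the 20 weeks of the study (Section 8.1) or of administration (Section 1), and Days 0, 28, 56, 84, 112 and 140 make exactly six. The session 0 label also fits.
- For screening: Section 3.1 pairs the baseline vulvoscopy with the baseline physical examination, which Appendix 1 schedules before dosing only at screening. This pointer is weak, because Section 3.1 also repeats the physical examination every 4 weeks, which Appendix 1 does not.

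The text leans to Day 0 without saying so.

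**The case against.** The strongest reply is that the SAP may already intend all visits to be scored. It gives the VGTA range per visit, and it has the photographs sorted by exam date without limiting which ones. A reader might infer the opposite, that the weeks 4 to 16 photographs were never scored or that the SAP cancels Section 8.2. Neither inference is supported. The one SAP sentence that says which photographs were scored names baseline and end of study, but nothing excludes the others, and Section 8.2 still stands. What remains is that the scoring is unclear, and that even if every visit was scored, no by-visit summary or improvement rule is given.

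Second, this is a 10-woman pilot meant to document change, and the SAP's title speaks of before and after 20 weeks, which fits a single pre/post test. That is a good reason not to add tests. It does not supply the table that the protocol promises.

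Third, the clinician's visual scale is already summarised by visit (Section 8.3). Its pallor, redness and dryness items match three vestibular VGTA items. The other 7 of 10 items, 7 × 3 = 21 of 30 points, have no such counterpart.

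Fourth, Section 5.5 introduces its field with the word including, which need not be exclusive, and Appendix 1 uses one photography row for all visits. It would be too strong to say that vaginal images will be lost. The texts conflict, and the loss is a worst case.

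Finally, a reader might infer that the swab baseline is equally open, or that the reader of the photographs saw the dates. The SAP places the baseline examination, with the swab test, at screening, so moving it would be a preference. Sorting by date does not establish that dates were visible; the plan simply does not describe masking of order.

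**Conclusion.** The conflict holds on the text. The plan describes a photographic score for 1 of the 5 comparisons in Section 8.1, leaving 4 of 5 (40 of 60 planned subject-timepoints, 67%) without one, and photographic improvement is undefined at every visit. The count assumes all 10 women complete all six timepoints and takes the SAP's sentence on scored photographs at face value.

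The Section 5.5 conflict puts at least 6 of 30 VGTA points at risk at four visits, but only on a literal reading. The baseline gap is one of labelling: Day 0 is favoured but not named, and the documents give no information on pre-dose change from which a bias could be inferred.

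This should be corrected. It does not call N = 10 or the single pre/post test into question.

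**What to change.** 1. **Section 5.5.** Reconcile its photographic field with Sections 3.1 and 8.1, so that vulva, vestibule and vagina are photographed at every session.
2. **SAP, scoring.** Have the existing reader score baseline and weeks 4, 8, 12, 16 and 20 on the VGTA, in shuffled order with dates hidden.
3. **SAP, analysis.** Keep baseline to week 20 as the only tested VGTA contrast. Report weeks 4 to 16 descriptively as the distribution of VGTA change, and use the proportions lower than, equal to and higher than baseline as the Section 8.2 table. The proportion lower should not stand alone: if reading noise is symmetric (an assumption, since the documents give no reliability data) and nothing truly changes, about half of the women without a tie would score lower by chance.
4. **Baseline.** State that Day 0 is the photographic baseline, and use one session numbering in Sections 1, 3.1 and 8.1.

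The cost is protocol and SAP wording, 4 × 10 = 40 more photograph sets for the same reader, and possibly a wider field at four existing visits. No visit or patient is added. The SAP is written in the past tense. If collection has ended, step 1 comes too late, but steps 2 to 4 can still be applied to stored photographs, with a statement of when the rules were fixed.

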8.3 Patient Reported Outcomes

Mean pain score will be summarized at each scheduled visit. Subjects will also be categorized at each visit as having more pain, the same pain, or less pain compared to baseline.

Mean scores will be summarized for each item of the visual scale at each scheduled visit. Subjects will also be categorized at each visit as worsened, unchanged, or improved compared to baseline for each item of the visual scale at each scheduled visit.

For each subject, the proportion of total sexual events with a 'yes' response since the last scheduled visit will be calculated for each diary question at each scheduled visit.

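### One reader scores the photographs on an unvalidated scale with no repeat reading described, so reading error is never estimated and one woman's VGTA change cannot be judged against it

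*SAP*

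**What the plan says.** Protocol section 3.4 describes the primary endpoint as photographs. Section 8.2 compares photographs across visits and tabulates the share of women improved at each one. It names no instrument and sets no threshold for improvement. The protocol does not mention the VGTA scale.

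The SAP supplies the scoring. Ten features of genital appearance are each rated on four points: "Each subject could score between 0 and 30 total points on the VGTA at each visit". It adds that "The VGTA scale has not been validated". The photographs are "assessed by the principal investigator, a sexual medicine physician, who had not examined any of the women in person", and "He assigned scores to the photographs using pre-determined Likert scales for the 10 parameters of VGTA scale". Beforehand, "the photographs were sorted by subject number and date of exam". Baseline and end-of-study scores are compared by a two-sided Wilcoxon signed-rank test at 0.05. The SAP describes no second reader, repeat reading, agreement statistic or measurement-error estimate.

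Separately, a clinician scores five vestibular signs in person on a 0-3 scale at every visit (protocol section 2, Appendices 1 and 3). Section 8.3 summarises these on their own: "Mean scores will be summarized for each item of the visual scale at each scheduled visit". Three of the five (pallor, redness, dryness) have VGTA counterparts (pallor, erythema, loss of moisture). No comparison between the two sources is described.

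On size, section 8.1 says: "The sample size of 10 menopausal Subjects was chosen for this study based on this being a pilot study". It gives no effect size, SD or power.

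**The concern.** A VGTA change score is the difference of two readings, and each carries the reader's own error. If every set is read once, that error cannot be separated from real differences between women in how much they changed. A reader of the results could not say whether a fall of 2, 4 or 6 points in one woman exceeds what the same person would record on looking again.

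A count of women improved is exposed in the same way if it is built on VGTA, because without a threshold any small fall counts. The group comparison is affected less: reading error widens the spread of the 10 differences and so costs power. For a pilot using a new scale, a repeatability figure would be one of its more useful results, and nothing planned would produce it.

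**Working it through.** **Inputs from the documents.** 10 women; 10 items scored 0-3; one reader; two time points; two-sided signed-rank test at 0.05. The stated range reproduces: 10 x 3 = 30. There is no sample-size calculation to reproduce.

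**Assumptions.** The documents give no reading error or SD of change. Let *s* be the within-reader SD of one total score, taken as 1, 2 or 3 points. Let the SD of true change be 3 points, with 6 as a second value. No dropout.

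**1. One woman's change.** The SD of a difference of two single readings is sqrt(2) x *s*. The smallest change outside reading error (95%) is 1.96 x sqrt(2) x *s*. With two averaged readings per set it is 1.96 x *s*.

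| *s* | Single reading | Mean of two |
|---|---|---|
| 1 | 2.8 | 2.0 |
| 2 | 5.5 | 3.9 |
| 3 | 8.3 | 5.9 |

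**2. Apparent improvement with no true change.** Treat the difference as normal with mean 0 and SD sqrt(2) x *s*, rounded to whole points. A fall of at least 1 point then has probability P(Z > 0.5 / (sqrt(2) x *s*)). This gives 36%, 43% and 45% for *s* = 1, 2, 3, or roughly 4 of 10 women. It applies only if improvement means any fall in VGTA, which the protocol does not say.

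**3. The group test.** With 10 pairs the exact two-sided test rejects at W <= 8, with size 0.0488. Ten items scored 0-3 in 10 women were simulated with no true change and random item error of SD 0.3 to 1.0. The false-positive rate was 4.5% to 5.0%, so random reading error does not inflate it. The cost is power: about 80% power needs a mean change near 1.02 SDs of the difference. If reading error were the only source of spread, that is 1.02 x sqrt(2) x *s* = 1.4, 2.9 or 4.3 points. Real variation between women would raise these figures.

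**4. Gain from a second reading.** Variance of change is SDtrue² + 2*s*² with single readings and SDtrue² + *s*² with two averaged.

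| *s* | Ratio, SDtrue = 3 | Reduction | Equivalent n (10 / ratio) | Reduction, SDtrue = 6 |
|---|---|---|---|---|
| 1 | 10/11 = 0.909 | 9% | 11.0 | 1 - 37/38 = 3% |
| 2 | 13/17 = 0.765 | 24% | 13.1 | 1 - 40/44 = 9% |
| 3 | 18/27 = 0.667 | 33% | 15.0 | 1 - 45/54 = 17% |

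**5. Why a repeat reading must be masked.** Suppose there is no true change, *s* = 2 and reading error is the only source of spread. Suppose also that knowing the visit order shifts the reader by 2 points between baseline and week 20. In simulation, p < 0.05 occurs in 50% of trials with one reading and 78% with two averaged. Averaging sharpens a biased estimate as readily as an unbiased one.

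**The case against.** A reader might infer that, with one reading on an unvalidated scale and only 10 women, no change in VGTA can be told apart from reading error. The documents do not support that. The SAP's stated VGTA inference is a paired group test. Random error is already in the spread of the differences, and step 3 shows that the test keeps its size. A small sample lowers power; it is not what leaves reading error unmeasured. Nor does lack of validation, which the SAP discloses itself, show that the scale repeats poorly.

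Other objections stand in part:

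- The thresholds in step 1 concern one woman, and the SAP makes no individual VGTA claim. The nearest use is the share improved in protocol section 8.2, which is not tied to VGTA. The point therefore applies there only conditionally.
- That each set is read once is inferred from silence. It is the plain reading, but the SAP does not state it.
- The SAP does not label VGTA the primary endpoint, and the study is a declared pilot. This lowers the stakes, but the remedy is small too.
- The precision gain rests on assumed SDs and independent errors. A reader who remembers a set will repeat the score, which flatters repeatability and reduces the real gain.
- Comparing VGTA with the in-person scores mixes differences of rater, of medium and of item definition, and covers 3 of 10 items. It cannot measure repeatability.
- Re-reading date-ordered photographs would leave any order-related bias in place. This is right, and it is why masking and random order belong in the fix.

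**Conclusion.** The concern holds in a limited form. As the plan is written, reading error is never estimated. One woman's VGTA change cannot be judged against it, and neither can a share improved if it is based on VGTA. The signed-rank test remains valid against random error and loses some precision.

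The individual thresholds of 2.8, 5.5 and 8.3 points follow from assumed reading SDs of 1, 2 and 3. The 9% to 33% cut in variance also assumes a true-change SD of 3 and independent readings. It is illustrative, is an upper bound if the reader remembers the sets, and falls to 3% to 17% if the true-change SD is 6. The case for change rests more on obtaining a repeatability figure than on the gain in precision. This is a cheap improvement to a pilot, not a fault that overturns its group analysis.

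**What to change.** Amend the SAP so that:

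- The same reader scores every baseline and week-20 set twice (10 women x 2 time points, about 20 sets), in separate sessions and without sight of the first scores.
- Subject and date labels are masked, and the sets are put in a fresh random order for each session.
- The mean of the two readings enters the Wilcoxon test.
- The within-reader SD of the total and the weighted kappa for each item are reported, and items that repeat poorly are flagged.
- Any statement that an individual woman improved is interpreted against that SD. If the share improved in protocol section 8.2 is to use VGTA, the SAP says so and gives the threshold.
- As a descriptive check only, VGTA pallor, erythema and moisture are cross-tabulated against in-person pallor, redness and dryness from the visit at which the photographs were taken. Because photographs and visual scale are both scheduled at screening and at Day 0, the SAP should say which visit is baseline.

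The cost is a second scoring of about 20 existing sets, someone to mask and shuffle them, and a few sentences in the SAP. No extra reader, visit or patient procedure is needed. The downside is reader time, and a more modest claim if repeatability proves poor.
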